8.7 Secondary endpoints

Clinical status at Day 7 and Day 14:

Change in clinical status between baseline and post-baseline will be modelled using regression models appropriate for ordinal data, adjusting for stratification factors, sex, and baseline CRP. Details will be provided in the SAP.

Percentages for each category of the ranking scale will be tabulated by treatment arm, along with differences between treatment arms at each time point. The proportion of subjects for each of the items in the scale will be compared using an adjusted risk difference obtained from a regression model, adjusting for stratification factors, sex, and baseline CRP. Full details of the regression model will be provided in the SAP.

Total number of study days: (a) free of oxygen supplementation; (b) in ICU; (c) of hospitalization; (d) free of respiratory failure; (e) alive: For each endpoint (a) - (e), a Poisson regression model or a negative binomial model will be used to assess the relationship with treatment, adjusting for stratification factors, sex, baseline CRP and number of days on study (as applicable). Details of the model, including censoring rules, if any, will be provided in the SAP.

[figure not shown]
Percentage of subjects discharged from the hospital: percentages of subjects discharged from the hospital will be tabulated by treatment arm, along with differences between treatment arms. The proportion of subjects will be compared using an adjusted risk difference obtained from a regression model, adjusting for stratification factors, sex, and baseline CRP. Full details of the regression model will be provided in the SAP.

[figure not shown]
All-cause mortality at Day 28: percentages of subjects will be tabulated by treatment arm, along with differences between treatment arms, at each time point. The proportion of subjects will be compared using an adjusted risk difference obtained from a regression model, adjusting for stratification factors, sex, and baseline CRP. Full details of the regression model will be provided in the SAP.

Incidence of AEs/SAEs: will be summarized by system organ class and preferred term and by treatment arm using percentages.

Incidence of clinically significant changes: Percentage of subjects with clinically significant changes in laboratory parameters, ECG, and vital sign measurements will be computed for each treatment arm along with associated 2-sided 95% Clopper-Pearson CI.

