2 STUDY OVERVIEW

2.1 Objectives and Endpoints

| Objectives | Endpoints |
|---|--|
| Primary | |
| To assess the efficacy of losmapimod compared with placebo for treatment of COVID-19 when administered concurrently with standard of care | Proportion of progressors to death or respiratory failure by Day 28 |
| Secondary | 
To evaluate the effect of losmapimod compared with placebo on clinical outcomes
 
Clinical status by Days 7 and 14 as measured on the 9-point WHO ordinal scale:
 
• (8) death• (7) ventilation plus additional organ support (vasopressors, renal replacement therapy, ECMO)• (6) Intubation and mechanical ventilation• (5) noninvasive ventilation or high-flow oxygen therapy• (4) oxygen therapy but not requiring high-flow or non-invasive ventilation• (3) hospitalized but not requiring oxygen therapy• (2) Discharged from the hospital but with limitation of activities |

| | |
|---|---|
| | 
• (1) Discharged from the hospital and without any limitation• (0) No clinical evidence of the disease |
| To assess the effect on clinical status of treatment with losmapimod compared with placebo | Total number of study days free of oxygen supplementation by Day 28 Total number of study days in ICU by Day 28 Total number of study days hospitalized by Day 28 Total number of respiratory failure-free study days by Day 28 Percentage of subjects discharged from the hospital by Day 28 |
| To assess the effect on survival following treatment with losmapimod compared with placebo | All-cause mortality at Day 28 Number of study days alive by Day 28 |
| To assess the safety and tolerability of losmapimod compared with placebo | Incidence of AEs and SAEs Incidence of clinically significant changes in laboratory parameters and vital sign measurements |
| To characterize changes in SARS-CoV-2 infection following treatment with losmapimod compared with placebo | Quantifiable viral RNA on Day 7 |
| | |

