3.1.8 Handling of Dropouts and Missing Data

All missing or incomplete safety and PD data, including dates and times, will be treated as such. Missing test results or assessments will not be imputed, and as such, are assumed missing completely-at-random (MCAR).

For laboratory data, values below the limit of quantitation (recorded as “< LLQ”) will be set to half that limit.

For the analysis of hospital-free and ICU-free days, subjects who die prior to the analysis time point will have post-death days considered to be not hospital-free and not ICU-free.

Adverse events with missing start dates will be considered as treatment-emergent unless the partial date excludes that possibility, e.g., the adverse event month is prior to the first dose of study drug. Otherwise, the first day of the month will be used to impute missing start days and January will be used to impute missing start months. For example, if the first dose of study drug was on January 8, 2021 and an adverse event started in January 2021 with missing day, the start date will be imputed as the first dose date (January 8, 2021) and this adverse event will be considered as treatment-emergent. In the same example, if another adverse event has start month of December 2020 with missing day (before the first dose date of January 8, 2021), its start date will be imputed as December 1, 2020 and will not be considered as treatment-emergent.

Subjects who terminate the study prior to the analysis time point, not due to death, will be considered as missing for the analysis of key efficacy endpoints. Missing data in each treatment arm will be imputed using the observed data in their respective arm under the missing at random (MAR) assumption. Multiple imputation (MI) will be performed using the fully conditional specification (FCS) model. The imputation model will include the stratification factors, sex, and baseline CRP.

The handling of missing data for the key efficacy endpoints are outlined as the following:

1. Primary endpoint: patients whose status could not be ascertained (lost-to-follow up, etc.) will be imputed using multiple imputation approach.
2. Change in Clinical Status at Days 7 and 14: missing clinical status at the post-baseline timepoint will be imputed using multiple imputation approach.

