3.4.2 Secondary Efficacy Endpoints

Clinical status at Day 7 and Day 14:

Change in clinical status between baseline and at Days 7 and 14 will be modeled using ordinal logistic regression models, adjusting for stratification factors, sex and baseline CRP. If the subject progresses to death and the value of WHO 9-point scale is missing, the missing value of WHO 9-point will be imputed as (8) death.

Percentages for each category of the ranking scale will be tabulated by treatment arm, along with differences between treatment arms at each time point. The proportion of subjects for each of the items in the scale will be compared using an adjusted risk difference obtained from an ordinal logistic regression model, adjusting for stratification factors, sex and baseline CRP.

Total number of study days by Day 28:

(a) Free of oxygen supplementation; (b) in ICU; (c) of hospitalization; (d) free of respiratory failure; (e) alive; For each endpoint (a) – (e), a Poisson regression model will be used to assess

the relationship with treatment, adjusting for stratification factors, sex, baseline CRP and number of days on study. The key study endpoint of “oxygen free days by Day 28” will be tested at 1-sided significance level of 0.025 as outlined in Section 3.1.5.

If a patient died, the number of days of (a)-(e) are considered as having the events on and after the patient died. For example, if a patient died on Day 6. The days from Day 6 and after are considered not free of oxygen supplementation, hospitalization, ICU, and respiratory failure.

Percentage of subjects discharged from the hospital by Day 28:

Percentages of subjects discharged from the hospital will be tabulated by treatment arm, along with differences between treatment arms. The proportion of subjects will be compared using an adjusted risk difference obtained from a logistic regression model, adjusting for stratification factors, sex, and baseline CRP.

The percentage of subjects discharged from the hospital is defined as the number of subjects discharged from the hospital divided by the sum of the number of subjects who completed the study and the number of subjects who died during the study period.

A sensitivity analysis will be performed by excluding the subjects who died after being discharged from the hospital from the numerator of the above percentage calculation.

Missing data will be imputed similarly as primary endpoint for the above endpoints.

All-cause mortality at Day 28:

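### SAP 3.4.2 adjusts days alive by Day 28 for number of days on study; if time on study ends at death, this removes the mortality effect the endpoint is meant to show

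*SAP*

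**What the plan says.** SAP 2.1 lists two endpoints under the survival objective: Day 28 all-cause mortality and "Number of study days alive by Day 28".

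SAP 3.4.2 groups the second with four other day counts ("e) alive; For each endpoint (a" to e) and gives them one method: "a Poisson regression model will be used to assess" each of them. The adjustment set follows in the same sentence: "the relationship with treatment, adjusting for stratification factors, sex, baseline CRP and number of days on study". Protocol 8.7 has the same list but qualifies the last term: "adjusting for stratification factors, sex, baseline CRP and number of days on study (as applicable". The SAP drops the qualifier, and SAP 6, which lists departures from the protocol, does not mention it.

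Neither document defines number of days on study or says whether it enters as an offset or as a covariate. Two SAP rules bear on its meaning:

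- SAP 3.1.8 gives a separate rule for "Subjects who terminate the study prior to the analysis time point, not due to death". That makes death one way of terminating the study.
- SAP 3.4.2 sets the outcome after death: "If a patient died, the number of days of (a)-(e) are considered as having the events on and after the patient died". This fixes what is counted as the outcome. It does not say what value the adjuster takes for a death.

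**The concern.** Days alive is shortened by death. If days on study is shortened by the same deaths, the model adjusts the outcome for a post-randomization copy of itself. As an offset, it compares days alive per day on study, which is about 1 in both arms. As a covariate, the term explains nearly all the variation and leaves treatment little to explain. The reported ratio would sit near 1.00 for a beneficial drug and for a harmful one, and it would appear beside a mortality analysis that it could seem to contradict.

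SAP 3.1.7 gives no relief: its convergence fallback removes sex and then the stratification factors, not days on study.

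**Working it through.** **Inputs.** From the documents: 205 per arm, one-sided 0.025, a 28-day horizon, and the SAP 3.4.2 model. Assumed, because the documents give no mortality rate: 20% on placebo against 12% on losmapimod (range 10% v 6% to 30% v 18%), with the day of death uniform over Days 2 to 28 (mean 15).

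**The plan's own figure.** There is none for this endpoint. The 205 per arm comes from the primary endpoint. For 30% against 18%, a fixed design gives 81.4% power, and the SAP futility boundaries give 79.4% to 80.2%. The stated 80% therefore reproduces.

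**Step 1: the identity.** A completer has 28 days alive and 28 on study. A death on Day d has d days on study and either d days alive (rule A, death day counted in both) or d − 1 (rule B, death day on study but not alive, which is closer to the SAP 3.4.2 rule).

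**Step 2: the effect to be estimated.**
- Rule A: placebo 0.80×28 + 0.20×15 = 25.40; losmapimod 0.88×28 + 0.12×15 = 26.44; ratio 1.041.
- Rule B: placebo 0.80×28 + 0.20×14 = 25.20; losmapimod 0.88×28 + 0.12×14 = 26.32; ratio 1.044.

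**Step 3: the same effect with log(days on study) as offset.** Ignoring baseline covariates, the estimate is the between-arm ratio of total days alive to total days on study.
- Rule A: (26.44/26.44) ÷ (25.40/25.40) = 1.000.
- Rule B: (26.32/26.44) ÷ (25.20/25.40) = 0.9955 ÷ 0.9921 = 1.003.

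**Step 4: simulation of the adjusted model** (strata, sex, log CRP; 300 trials per scenario; 20% v 12%).

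| Days-on-study term | Rule | Mean ratio | Rejects, model-based SE | Rejects, robust SE |
|---|---|---|---|---|
| none | A | 1.041 | 52% | 46% |
| none | B | 1.045 | 62% | 51% |
| log offset | A | 1.000 | 0% | not meaningful: no residual variation |
| log offset | B | 1.003 | 0% | 64% |
| linear covariate | A | 0.997 | 0% | 0% |
| linear covariate | B | 0.998 | 0% | 0.3% |

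From 10% v 6% to 30% v 18%, the model without the term gives ratios of 1.021 to 1.071, with power of 13% to 84% (model-based) or 25% to 68% (robust). With the term, model-based rejections are 0% throughout, even at 30% v 0%, where the ratio without the term is 1.16 to 1.18. With 5% non-death dropout imputed as alive, the ratio is 1.004 to 1.016 and model-based rejections are at most 3%.

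**Step 5: the standard error once the term is removed.** Take rule A with 20% mortality in both arms.
- Variance among deaths: (27² − 1)/12 = 60.67.
- Total variance: 0.20×60.67 + 0.20×0.80×13² = 39.17.
- Poisson assumes a variance equal to the mean, 25.40. The ratio is 39.17/25.40 = 1.54, so z is inflated by √1.54 = 1.24.
- One-sided type I error: P(Z > 1.96/1.24) = P(Z > 1.58) = 5.7%. Simulation gives about 5% to 6%.

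The 52% and 62% model-based figures above are therefore flattering. The robust figures are the fair benchmark.

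**The case against.** The strongest objection is that the result rests on a term nobody has defined. If deaths were assigned 28 days, the adjuster would be constant for deaths and completers, the model would behave as if the term were absent, and the problem would vanish. The SAP does assign values to days after death, which fits counting to a fixed horizon, and SAP 7 leaves programming detail to a separate document. This stands as a limit on certainty. It does not settle the matter, because the post-death rule governs the outcome and SAP 3.1.8 points towards time on study ending at death.

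A second objection is that SAP 6 does not list removal of the protocol's qualifier, so the shorter sentence may be only an abbreviation. That is possible. A reader might infer a deliberate decision to force the term onto days alive; the documents do not show one. The SAP still applies the model to all five endpoints as written.

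Third, the test is not always powerless. Under rule B, an offset model with a robust standard error rejects often (64% at 20% v 12%). This is correct, but those rejections come only from the one-day counting difference, and the estimate of about 0.3% says nothing useful about days alive.

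Fourth, the consequence is small. Days alive is not among the four endpoints in SAP 3.1.5. SAP 3.4.2 compares Day 28 mortality by logistic regression without this term and plans survival methods for time to death. This stands.

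**Conclusion.** The point holds as a defect in the written model for one secondary endpoint. On the reading best supported by SAP 3.1.8, the treatment ratio for days alive is about 1.00 whatever the mortality effect, and with model-based Poisson standard errors it is essentially never significant. At 20% v 12% mortality the same data without the term give a ratio of about 1.04 and 46% to 51% power with a robust standard error. The sizes rest on assumed mortality and an assumed uniform day of death. The near-unit ratio needs only that time on study ends at death and that non-death dropout is small.

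Two stronger conclusions are tempting and not supported. A reader might infer that the trial could miss, or be read as denying, a survival effect; the separate mortality and time-to-death analyses prevent that. A reader might also extend the identity to oxygen-free days, a key endpoint with the same adjuster. Oxygen-free days do not equal days on study, so this argument does not carry over, although the term's definition matters there too.

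**What to change.** In SAP 3.4.2, remove number of days on study from the model for endpoint (e). Alternatively, restore the protocol's qualifier and set the denominator at 28 days for deaths. Either way, define the term and state whether it is an offset or a covariate wherever it is kept.

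Keep the planned multiple imputation for subjects who leave alive. Specify a robust or overdispersion-corrected standard error for (e), because the model-based Poisson error does not hold the one-sided 2.5% level at the higher mortality rates. Restricted mean survival time to Day 28 with the same baseline adjusters is an optional alternative and is not needed to cure the defect.

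The cost is a sentence or two of SAP text and a few lines of code, with no new data or patients. It should be settled before unblinding.

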3. Oxygen-free, ICU, hospitalized, respiratory failure-free days: subjects who die prior to the analysis time point will have post-death days considered not event free. For example, if a subject died on Day 6, Day 6 and after will not be counted toward oxygen-

free, ICU, hospitalized, respiratory failure-free days. Subjects who terminate the study for other reasons prior to the analysis time point will be imputed using multiple imputation approach.

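### The Day 6 example in SAP 3.1.8 item 3 leaves post-death days out of the ICU-day and hospital-day counts, against the rest of the SAP, so early death can look like less use of care

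*SAP*

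**What the plan says.** SAP 2.1 names the endpoints "Total number of study days in ICU by Day 28" and "Total number of study days hospitalized by Day 28". Both count time spent in a bad state.

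Four statements in the SAP bear on the days after a death:

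- SAP 3.1.8, general text: "subjects who die prior to the analysis time point will have post-death days considered to be not hospital-free and not ICU-free".
- SAP 3.1.8, lead sentence of item 3: "subjects who die prior to the analysis time point will have post-death days considered not event free".
- SAP 3.1.8, example in item 3: "if a subject died on Day 6, Day 6 and after will not be counted toward oxygen", and the list continues, running into the next sentence, "free, ICU, hospitalized, respiratory failure-free days. Subjects who terminate the study for other reasons". That next sentence sends dropouts for reasons other than death to multiple imputation.
- SAP 3.4.2: "If a patient died, the number of days of (a)-(e) are considered as having the events on and after the patient died". Its own Day 6 example classes the days from Day 6 as free of none of the four states: oxygen, hospital, ICU or respiratory failure.

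SAP 3.4.2 analyses each count by Poisson regression, adjusted among other things for the number of days on study. It does not say whether that term is an offset or a covariate, or how it is counted for a subject who dies. Protocol 8.7 leaves model and censoring details to the SAP, and SAP section 6 lists no change on this point.

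**The concern.** Leaving out post-death days penalises death when the count is of good days (oxygen-free, respiratory failure-free). It does the opposite when the count is of bad days. Under the item 3 example a subject who dies on Day 6 has at most 5 ICU days and scores better than a survivor who needed 10.

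Death is a component of the primary endpoint, so a rule for post-death days will be needed. Two programmers working from the two sections would report different results for (b) and (c) from the same data. If the rule were settled after unblinding, the choice would be open to influence by the results.

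**Working it through.** The plan states no expected value for these endpoints, so its own Day 6 example is the starting point.

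**Step 1: one subject, no outside assumptions beyond the stay before death.** With death on day D, the two instructions differ by 28 − D + 1 days. For D = 6 that is 23 of 28 days.

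- In hospital and ICU every day before death: the item 3 example gives D − 1 = 5 ICU and 5 hospital days; 3.4.2 gives 5 + 23 = 28 and 28.
- Never in ICU before death: 0 ICU days against 23.

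For oxygen-free and respiratory failure-free days the two sections agree: nothing is credited from Day 6.

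**Step 2: arm means.** The documents give no mortality, length of stay or day of death. Assumed: 30% of subjects need ICU; ICU survivors spend 14 days in ICU and 20 in hospital; the other 70% spend 8 days in hospital; all deaths are among the ICU subjects, who are in ICU and hospital until death. With mortality m:

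- Item 3 example: ICU = m(D − 1) + (0.30 − m)·14; hospital = m(D − 1) + (0.30 − m)·20 + 0.70·8.
- SAP 3.4.2: the same, with 28 in place of D − 1.

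For m = 0.10 on placebo, 0.15 on losmapimod and D = 6:

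- ICU, item 3 example: 0.50 + 2.80 = 3.30 against 0.75 + 2.10 = 2.85; ratio 0.864.
- ICU, 3.4.2: 2.80 + 2.80 = 5.60 against 4.20 + 2.10 = 6.30; ratio 1.125.
- Hospital, item 3 example: 10.10 against 9.35; ratio 0.926.
- Hospital, 3.4.2: 12.40 against 12.80; ratio 1.032.

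If days on study stop at death and enter as an offset, mean exposure is 0.10·5 + 0.90·28 = 25.70 and 0.15·5 + 0.85·28 = 24.55. The ICU ratio under the item 3 example becomes (2.85/24.55)/(3.30/25.70) = 0.904. The artefact shrinks but stays.

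**Step 3: range.** Drug-to-placebo ratios under the item 3 example, over mortality of 5% v 10%, 10% v 15% and 10% v 20% (placebo v drug):

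| Day of death | ICU | ICU, offset | Hospital | Hospital, offset |
|---|---|---|---|---|
| 6 | 0.727–0.880 | 0.799–0.919 | 0.851–0.931 | 0.935–0.973 |
| 10 | 0.865–0.937 | 0.933–0.971 | 0.895–0.950 | 0.966–0.985 |
| 14 | 0.976–0.988 | 1.016–1.034 | 0.936–0.969 | 0.992–0.996 |
| 20 | 1.053–1.106 | 1.071–1.144 | 0.991–0.996 | 1.012–1.025 |

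Under 3.4.2, with no offset, the ratios are 1.125–1.250 for ICU and 1.032–1.065 for hospital, whatever the day of death.

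**Step 4: turning point.** Each extra death replaces a stay of L days by D − 1 days, so without an offset the sign reverses only if D − 1 < L: before Day 15 for ICU (L = 14) and before Day 21 for hospital (L = 20). With the offset the turning point comes earlier, between Days 10 and 14 for ICU and between Days 14 and 20 for hospital.

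**Step 5: exposure under 3.4.2.** A death on Day 6 carries up to 28 ICU days. If days on study stop at death, exposure is about 5 days, and the count exceeds it.

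**The case against.** The SAP is not evenly divided. The general text of 3.1.8, the lead sentence of item 3 and 3.4.2 all treat post-death days as not free of ICU or hospital; only the item 3 example departs. Its list mixes '-free' terms with bare ones, and the lead sentence speaks of event-free days, so a dropped '-free' is a natural explanation. This stands as to intent. It does not remove the defect, because ICU and hospitalized are the endpoint names in SAP 2.1 and an analyst following the example as written would leave the days out.

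A reader might infer that a harmful drug could emerge from this trial looking beneficial. The documents do not support that. ICU and hospital days are not among the four endpoints in the fixed sequence of SAP 3.1.5. Oxygen-free days, which are, get the same treatment in both sections. Death is part of the primary endpoint, and SAP 3.4.2 analyses mortality separately, with survival methods as sensitivity analyses. The reversal also depends on early deaths under assumed lengths of stay.

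A reader might also infer from 3.4.2, which covers all of (a)-(e), that every subject who dies is credited with 28 days alive. The same literal reading would make post-death days oxygen-free, which the example in 3.4.2 rules out. The example is silent on (e), so this is loose wording to tidy rather than a rule.

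**Conclusion.** The point holds as a drafting error in the SAP 3.1.8 item 3 example, which should be fixed before unblinding. The contradiction for ICU and hospital days, and the gap of 23 days for a death on Day 6, follow from the SAP's own text. The ratios rest on assumed mortality, ICU share and lengths of stay, so they show that a sign change is possible, not that it is expected. What is exposed is two supportive secondary results that would be reported beside the mortality analysis.

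**What to change.** Before unblinding:

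1. Reword the example in SAP 3.1.8 item 3 to agree with 3.4.2: from the day of death through Day 28, days are not oxygen-free and not respiratory-failure-free, and they count as ICU and hospital days. Keep ICU and hospitalized days within item 3, because its multiple-imputation rule for non-death dropouts must still cover them.
2. In SAP 3.4.2, restrict the death rule to (a)-(d) and state that days alive (e) stop at death.
3. For (a)-(d), take the number of days on study through Day 28 for subjects who die, so that no count exceeds its exposure.

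This costs SAP wording only: no new data, and the protocol's endpoints keep their names.

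Recasting the endpoints as ICU-free and hospital-free days is not an interchangeable option. In the Step 2 case under 3.4.2, ICU-free means would be 28 − 5.60 = 22.40 and 28 − 6.30 = 21.70, a ratio of 0.969, whereas the reciprocal of 1.125 is 0.889. It would also change endpoints named in the protocol.

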3.2.2 Safety Analysis Set

The Safety Analysis Set is defined as all subjects who receive any study drug. All analyses using the Safety Analysis Set will group subjects according to treatment actually received. The Safety Analysis Set will be used for all safety and tolerability analyses.

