Percentages of subjects will be tabulated by treatment arm, along with differences between treatment arms, at each time point. The proportion of subjects will be compared using an adjusted risk difference obtained from a logistic regression model, adjusting for stratification factors, sex, and baseline CRP.

Standard survival analysis methods will be used as sensitivity analyses to compare the time to each of these clinical events of interest (death and respiratory failure) as well as the composite thereof. Specifically, the cumulative incidence rates between two groups at Day 28 will be compared, accounting for potential differential follow-up.

Incidence of AEs/SAEs by Day 28: will be summarized by system organ class and preferred term and by treatment arm using percentages.

Incidence of AEs/SAEs is calculated by the number of subjects who developed AEs/SAEs during the study divided by the sum of the number of subjects who completed the study and the number of subjects who died during the study period. (see above edit)

Incidence of clinically significant changes by Day 28: Percentage of subjects with clinically significant changes in laboratory parameters, ECG, and vital sign measurements will be computed for each treatment arm along with associated 2-sided 95% Clopper-Pearson CI.

Changes in the assessments will be considered as clinically significant if the Baseline assessment is not clinically significantly abnormal and there has been at least one occurrence of post-Baseline assessments with a clinically significant abnormal result by Day 28.

[figure not shown]
Death is not considered a form of missing data or censoring. The incidence of clinically significant changes is calculated by the number of subjects with clinically significant changes during the study divided by the sum of the number of subjects who completed the study and the number of subjects who died during the study period.

Clearance of quantifiable viral RNA by Day 7: percentages of subjects with clearance of quantifiable viral RNA will be tabulated by treatment arm, along with differences between treatment arms, at each time point. The proportion of subjects will be compared using an adjusted risk difference obtained from a logistic regression model, adjusting for stratification factors, sex, and baseline CRP.

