3.5 Safety Assessment

3.5.1 Adverse Events (AEs)

The latest version of Medical Dictionary for Regulatory Activities (MedDRA) will be used for the coding of AEs.

Treatment-emergent AEs will be defined as an event that occurs on or after the first dose of study drug or the worsening of a preexisting condition on or after the first dose of study drug. If a subject does experience an event both prior to and after starting administration of a treatment, the event will be considered a TEAE (of the treatment) only if it has worsened (i.e., it is reported with a new start date and the event is worsened in severity or becomes serious) after starting administration of the specific treatment, and prior to the start of another treatment, if any. All TEAEs collected during the investigational period will be summarized.

A summary overview of TEAEs will be provided, which presents the number of events and the number and percentage of subjects in each treatment group from the Safety Analysis Set for each of the following categories:

- TEAEs (overall, by maximum severity, and by maximum drug relatedness)
- Study drug-related TEAEs (overall and by maximum severity)
- All treatment-emergent adverse events of special interest (AESI)
- All treatment-emergent serious AEs (TESAEs)
- All study drug-related TESAEs
- TEAEs leading to death
- TEAEs leading to study drug discontinuation
- Study drug-related TEAEs leading to study drug discontinuation
- TEAEs leading to study drug interruption
- Study drug-related TEAEs leading to study drug interruption

The number of TEAEs and the number of subjects with at least 1 TEAE will be summarized by treatment group for each of the categories in the overview.

All AEs will be displayed in listings. In addition, SAEs and TEAEs leading to study drug discontinuation will be listed.

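### Three tabulated percentages in SAP 3.4.2 count surviving early leavers in the numerator but not in the denominator

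*SAP*

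**What the plan says.** SAP 3.4.2 builds three tabulated percentages in the same way.

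- **AE/SAE incidence** takes all "subjects who developed AEs/SAEs during the study divided by the sum of the number of subjects who completed the study and the number of" deaths in the study period.
- **Clinically significant changes** have the same denominator, with an "associated 2-sided 95% Clopper-Pearson CI" for each arm. A change counts only "if the Baseline assessment is not clinically significantly abnormal" and a later assessment is.
- **Hospital discharge** is "the number of subjects discharged from the hospital divided by the sum of the number of subjects who completed the study" plus deaths. The same section adds: "Missing data will be imputed similarly as primary endpoint for the above endpoints".

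No numerator is restricted to completers and deaths.

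Elsewhere the SAP takes a different line. Section 3.2.2 states: "The Safety Analysis Set will be used for all safety and tolerability analyses". Section 3.5.1 reports TEAEs as the "number and percentage of subjects in each treatment group from the Safety Analysis Set". Protocol 8.1.3 also assigns safety to that set. SAP section 6, which lists changes from the protocol, does not mention a completers-plus-deaths denominator.

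**The concern.** A treated subject can complete the study, die, or leave alive before Day 28. The third group is missing from the denominator but not from the numerator. The SAP expects such subjects. Section 3.1.8 says: "Subjects who terminate the study prior to the analysis time point, not due to death, will be considered as missing". The imputation model in 3.4.1.1 even carries a factor for having been discharged before leaving the study, which is exactly the subject who breaks the discharge ratio.

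Safety and tolerability is a stated secondary objective. Taken literally, the plan would overstate AE/SAE incidence and the rate of clinically significant changes. It would compute an exact binomial interval on counts that are not binomial. It would also use a different denominator for AE tables under 3.4.2 than for TEAE tables under 3.5.1. If early departure differs between arms, the tabulated rates would show an arm difference where none exists. The tabulated discharge percentage would not agree with an analysis that imputes the missing outcomes.

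**Working it through.** The plan states no figure that depends on these denominators, so there is none to reproduce. The check is algebra plus worked examples.

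**Inputs.** 205 subjects per arm (SAP 2.2.4). The share leaving alive before Day 28 and the event rates are not in the documents. I assume d = 2% to 20% and show event rates of 20%, 50% and 60%.

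**Formula.** Let N be the number treated, T the number who leave alive early, d = T/N, and x the number of all treated subjects with the event.

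- SAP 3.4.2 as written: x/(N − T)
- Safety Analysis Set: x/N
- Ratio of the two: N/(N − T) = 1/(1 − d)

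The multiplier does not depend on who has the event.

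| d | 1/(1−d) | 60% becomes | 20% becomes |
|---|---|---|---|
| 0 | 1.00 | 60.0% | 20.0% |
| 2% | 1.02 | 61.2% | 20.4% |
| 5% | 1.05 | 63.2% | 21.1% |
| 10% | 1.11 | 66.7% | 22.2% |
| 20% | 1.25 | 75.0% | 25.0% |

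**Three readings of one arm.** Take 205 treated and 20 early leavers, 16 of them with an AE. Of the other 185, 111 have an AE. The total with an AE is 16 + 111 = 127.

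- As written: 127/185 = 68.6%
- Safety Analysis Set: 127/205 = 62.0%
- Leavers removed from both sides: 111/185 = 60.0%

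The last is a proper proportion, but it discards 16 subjects' observed AEs.

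**Clopper-Pearson interval.** Take 41 subjects with a clinically significant change, 20 early leavers, and all 205 eligible at baseline.

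- As written: 41/185 = 22.2% (95% CI 16.4% to 28.8%)
- Safety Analysis Set: 41/205 = 20.0% (95% CI 14.8% to 26.1%)

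The first interval can be calculated, but it treats the 41 as a subset of the 185, which they are not if any leaver had the event.

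**Between arms.** Suppose both arms have a 50% event rate.

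- d = 5% and 15%: 0.50/0.95 = 52.6% and 0.50/0.85 = 58.8%, a spurious difference of 6.2 points
- d = 5% and 10%: 52.6% and 55.6%, a spurious difference of 2.9 points

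**Values above 100%.** These need x > N − T, so leavers with the event must outnumber completers and deaths without it. With equal risk p this means p > 1 − d: above 95% at d = 5%, above 80% at d = 20%. For example, 195 discharged with 20 leavers gives 195/185 = 105.4%, against 195/205 = 95.1%. This is an extreme case.

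**The case against.** **The intended population may be subjects with a known Day 28 outcome.** SAP 3.4.2 says death is not a form of missing data, which explains adding deaths to completers. On that view the numerator should be limited to the same subjects, and the interval is then valid. But the text does not limit it. Doing so would drop observed safety events in people who left, and it would still conflict with 3.2.2.

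**The size may be small.** Protocol 3.4.2 keeps subjects in follow-up after stopping drug, follow-up is 28 days, and visits can be remote. At d = 2% a 60% rate moves by 1.2 points. This stands: the size is unknown and could be about one point. With equal d in both arms the ratio of the arms is unchanged.

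**The two AE tables do not measure the same thing.** AEs are collected from consent, whereas 3.5.1 covers treatment-emergent events only, so their percentages could differ even with one denominator. This stands, but it does not explain or justify the different denominator.

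**The discharge conflict may be only an ambiguity.** A percentage among subjects with known outcome can sit beside an imputed, model-based comparison. That is fair as to purpose. The stated ratio is still faulty, because a discharged subject who then leaves has a known outcome and is excluded from the denominator.

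**Completer status.** The SAP does not define it. Protocol 8.4 ties it to the last PD assessment, so a subject followed to Day 28 who missed that sample could also leave the denominator. The PD sampling schedule is not visible in the public text, so this cannot be sized.

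**Conclusion.** The concern holds. As written, the three percentages are not proportions whenever a survivor with the event leaves early, and the exact interval for clinically significant changes then has no valid basis. The inflation is exactly 1/(1−d) relative to the all-treated rate: about 2% at d = 2%, 11% at d = 10% and 25% at d = 20%, all in relative terms. The values of d and the event rates are assumptions, and with no early leavers there is no error.

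The reach is limited. The adjusted comparisons in 3.4.2 are not clearly affected, the TEAE overview in 3.5.1 already uses the right set, and none of the three is a key endpoint under SAP 3.1.5. It should be corrected, but it does not threaten the primary result.

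**What to change.** Use one population above and below the line for each percentage.

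- **AE/SAE incidence:** divide by all Safety Analysis Set subjects, by treatment received.
- **Clinically significant changes:** divide by Safety Analysis Set subjects whose baseline for that parameter is not clinically significantly abnormal, keeping those who died or left early. State how a missing baseline is handled. This counts unobserved follow-up as no event and can understate Day 28 incidence, so give the number who left early beside each rate.
- **Discharge:** tabulate over the full FAS with the multiple imputation already specified.
- **Drafting:** remove the stray bracketed editing note after the AE/SAE formula.
- **Check viral clearance:** its denominator is subjects in the study by Day 7 plus deaths by Day 7. Protocol Table 1, footnote 7, allows the sample earlier at discharge. Leaving hospital is not leaving the study, but a subject who cleared and then left the study before Day 7 could be in the numerator only.

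The cost is three or four sentences of SAP text. No new data are needed and the primary analysis is untouched.
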